4.7.2 Analysis of Primary Outcome

To test the primary hypothesis that there will be a difference between the SparkRx and eUC arms such that participants randomized to receive SparkRx will have lower PHQ-8 scores at post-intervention, we will implement a mixed effect model with appropriate correlation matrix. Time (i.e., day after Baseline session [T=0] that each PHQ-8 was completed), intervention arm, time by intervention interaction, baseline PHQ-8 score, and antidepressant medication status (variable used for randomization) will be included in the model as fixed effects. We will test different correlation matrices such as UN, CS, AR(1), and select the best correlation

structure for our data. The hypothesis will be tested as two-sided with a significance level of 0.05. This primary analysis will be conducted according to the ITT principle with participants analyzed and outcomes attributed according to the treatment arm to which the participants were randomized, regardless of post-randomization compliance. We will additionally determine whether the stated threshold for clinically-meaningful reduction in severity based on PHQ-8 (reduction in score ≥ 5 from baseline) is included or surpassed by 95% confidence intervals around the average PHQ-8 reduction in the SparkRx arm.

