4.1 Primary Outcome

- The primary outcome measure is depressive symptom severity (PHQ-8 score), which will be used to compute differences in mean depressive symptoms between participants randomized to the SparkRx condition and those randomized to the eUC condition at post-intervention (5 weeks). PHQ-8 score will also be used to determine whether there is clinically-meaningful reduction in severity in the SparkRx group at post-intervention. Clinically-meaningful reduction in severity is defined as a 5 point or greater decrease in PHQ-8 score from baseline.

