4.6 Sample Size

Sample size calculation is based on primary outcome PHQ-8 at post-intervention. Six PHQ-8 measurements will be collected from each subject (baseline and weekly during the 5-week intervention period). Using a two-sample t-test approach, assuming a two-tailed alpha set at 0.05, a total of 200 participants (100 in each study arm) will give us 80% power to detect a moderate effect size of at least $d=0.4$. Given an anticipated 10% rate of attrition, we aim to enroll 220 total participants in the study.

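### The 5-point check in section 4.7.2 is satisfied once the upper 95% limit of the SparkRx mean reduction reaches 5, so observed means near 4 can pass and poorer precision makes passing easier

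*Combined protocol and SAP*

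**What the plan says.** Section 4.1 (Primary Outcome) names the between-arm difference in PHQ-8 at 5 weeks as the primary outcome, then adds a second use of the score: "PHQ-8 score will also be used to determine whether there is clinically-meaningful reduction in severity in the SparkRx group at post-intervention". The criterion follows: "Clinically-meaningful reduction in severity is defined as a 5 point or greater decrease in PHQ-8 score from baseline".

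Section 4.7.2 (Analysis of Primary Outcome) gives the method. After the mixed-model comparison of the arms, the team will see whether the 5-point threshold "is included or surpassed by 95% confidence intervals around the average PHQ-8 reduction in the SparkRx arm".

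Nothing in the document requires the point estimate or the lower limit to reach 5. It does not ask for the same interval in the eUC arm, does not call the result descriptive, and does not say whether the interval comes from raw change scores or from the mixed model. Separately, sections 4.2 and 4.7.3 compare the proportion of participants with a reduction of at least 5 points between arms by chi-square test.

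**The concern.** Section 4.1 asks whether a reduction of at least 5 points occurred. The rule in section 4.7.2 answers a different question: whether such a reduction can still not be excluded. Those are opposite ends of the confidence interval. Under the rule as written, the report could say that the protocol's threshold was reached when both the observed and the true mean reduction fall short of it. Dropout or noise would help rather than hinder.

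The quantity is also a pre-post change in one arm. Entry requires a PHQ-8 of at least 5 at screening (section 2.5), and Table 1 shows no separate participant PHQ-8 at the baseline visit, so the screening score appears to serve as baseline. Selecting on that score builds some regression to the mean into the change. Natural recovery and usual care (section 3.3) add to it. Because the check sits in the primary outcome section, its result is likely to be reported beside the primary result.

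**Working it through.** **1. The plan's own sample size.** Section 4.6 uses d = 0.4, two-sided alpha 0.05 and 80% power. The normal approximation gives 2 × (1.96 + 0.8416)² / 0.4² = 98.1, so 99 per arm; exact t-test power at 100 per arm is 0.804. The stated 200 in total is reproduced. Enrolling 220 gives 110 per arm, and 10% attrition leaves 110 × 0.9 = 99 evaluable per arm. That is the n used below.

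**2. What the rule amounts to.** Let L and U be the 95% limits for mean reduction.
- Included: L ≤ 5 ≤ U.
- Surpassed: L > 5.
- Either one: U ≥ 5.

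This follows from the wording and needs no SD. Since U = mean + 1.96 × SE, the smallest passing mean is 5 − 1.96 × SE, which falls as SE rises.

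**3. Inputs for size.** The SD of PHQ-8 change is not in the documents; I assume 5, with a range of 4 to 6. SE = SD/√n. The interval is taken as that of a raw mean change, with a normal approximation.

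**4. Chance of passing**, with true mean reduction μ:
- Rule as written: P = 1 − Φ((5 − 1.96·SE − μ)/SE)
- Lower-limit rule: P = 1 − Φ((5 + 1.96·SE − μ)/SE)

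Results at n = 99:

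| SD | SE | Smallest passing mean | P, μ = 4.0 | P, μ = 4.5 | Lower-limit rule, μ = 4.5 |
|---|---|---|---|---|---|
| 4 | 0.402 | 4.21 | 29.9% | 76.3% | 0.07% |
| 5 | 0.503 | 4.02 | 48.8% | 83.3% | 0.16% |
| 6 | 0.603 | 3.82 | 61.9% | 87.1% | 0.26% |

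Worked line for SD 5: 5 − 1.96 × 0.503 = 4.02. At μ = 4.0, z = (4.015 − 4.0)/0.503 = 0.03, so P = 48.8%.

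A simulation with t-based intervals (n = 100, SD 5, 100,000 runs) gave 49.4% at μ = 4.0 and 83.5% at μ = 4.5, in line with the table.

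**5. Effect of precision, SD 5.**

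| Evaluable in arm | Smallest passing mean | P, μ = 4.0 |
|---|---|---|
| 110 | 4.07 | 44.5% |
| 99 | 4.02 | 48.8% |
| 80 | 3.90 | 56.8% |

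Losing participants lowers the bar and raises the pass rate.

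**6. Cost of a lower-limit rule.** For about 80% chance of passing, μ = 5 + (1.96 + 0.84) × SE, which is 6.13, 6.41 and 6.69 for SD 4, 5 and 6.

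**The case against.** The best counter-argument is about reading. Section 4.7.2 never says what conclusion follows if 5 lies inside the interval, and a careful report could simply state where 5 falls and show the limits. That is possible. But section 4.1 gives the purpose as to "determine whether there is clinically-meaningful reduction in severity in the SparkRx group at post-intervention", and section 4.7.2 treats *included* and *surpassed* alike, so a pass in either case is the natural reading. If something else is meant, the text has to say so.

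Several limits on size stand:
- The SD is assumed, so *near 4* is illustrative; the direction of the flaw is not.
- At the planned 10% attrition the precision effect is small (4.07 to 4.02). The drop to 80 evaluable is a loss of 27% (30/110).
- A mixed-model interval could be somewhat narrower or wider, which would move the cut-off.
- The lower-limit rule is strict. At SD 5 and n = 99 a true mean of exactly 5 would pass about 2.5% of the time. A point-estimate rule lies in between: at a true mean of 4.5 it passes with probability 1 − Φ(0.5/0.503), about 16%.

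It is also fair that the check is additional, that the text makes no causal claim from it, and that the between-arm responder comparison gives readers a better guide. That comparison concerns individual responders, however, and does not correct a wrong statement about the arm mean. The SAP promised in section 4.7 could settle the matter, but nothing in the current text does.

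**Conclusion.** The concern holds. That the rule reduces to the upper limit reaching 5, and that imprecision helps it pass, follows from the wording of section 4.7.2, read with section 4.1 as a decision on whether a meaningful reduction occurred. At the planned size, means roughly 0.8 to 1.2 points below the protocol's own threshold would pass if the SD of change is 4 to 6 and the interval is that of a raw mean.

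The consequence is limited to a potentially misleading statement about the size of change in the SparkRx arm. The primary between-arm test, its error rate, the sample size and the responder comparison are untouched. It should be fixed, because the rule as stated gives the wrong answer to the question section 4.1 asks.

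**What to change.** In section 4.7.2, or in the SAP still to be written, delete *included or* and substitute text such as:

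> The 5-point threshold is met only if the lower limit of the 95% confidence interval for mean PHQ-8 reduction in the SparkRx arm is at least 5. Otherwise the mean and interval are reported without a met or not-met label. The same interval is reported for eUC. This within-arm result is descriptive and includes natural recovery and regression to the mean. Any claim that SparkRx causes meaningful improvement rests on the between-arm PHQ-8 difference (4.7.2) and the between-arm responder comparison (4.7.3).

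State also whether the interval is raw or model-based. If the sponsor finds the lower-limit rule too strict, reporting the mean and interval for both arms with no label at all also removes the problem.

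The cost is a few sentences, with no change to data collection, sample size or the primary test. The downside is a harder within-arm claim: about 80% chance of meeting it needs a true mean reduction near 6.4 (6.1 to 6.7). The lower limit does not remove regression to the mean, so the descriptive label and the eUC interval are needed with it.

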4.7.3 Analysis of Secondary Outcomes

We will compute the number and proportion of participants meeting criteria for intervention response, remission, and clinically-meaningful reduction in severity at post-intervention for each group, and compare rates between groups using chi-square tests. We hypothesize that there will be higher rates of intervention response, remission, and clinically-meaningful reduction in severity in the SparkRx arm than in the eUC arm.

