Participants will be asked to indicate in weekly participant symptom checks (PSCs; see Appendix 1) or to notify the study team if their treatment for symptoms of depression or any other health condition changes during the study, or if they participate in any other treatment/intervention research study. Participants will be encouraged to follow the advice of their doctor regarding all medical decisions. Participants will be told that this is a blinded study, meaning that most of the study staff with whom they interact after randomization will not know whether they received the SparkRx app or not. They will be provided with contact information if they need to reach out for app or web portal troubleshooting, or with questions about their participation in the study.

After eligibility is confirmed, an account for legal guardians (if applicable) in the secure web portal will be created with usernames (user email addresses), and legal guardians will be provided a temporary password to log in to change their password. Participants and legal guardians (if applicable) will be directed to complete baseline assessments in the secure web portal. Upon completion of baseline assessments, participants will be randomized (1:1) to either the SparkRx condition or the eUC only condition (see descriptions below). Randomization will be stratified by participant-reported antidepressant medication status ([yes, no] from the Medication Use Screener) and participant-reported baseline PHQ depression severity (low: PHQ-8 score <15; high: PHQ-8 score ≥15). Participants will receive instructions on how to download and log into their assigned mobile app. Following randomization and app download, the session will end. Additional information will be sent to participants via email.

Following the videoconferencing session, research coordinators will contact participants' healthcare provider offices and indicate that the patient has enrolled in this research study. If information is volunteered to the research coordinator that the participant is not a patient of the healthcare provider, the participant will be contacted to provide information for an alternative healthcare provider. As participant safety may be compromised in the absence of a known U.S.-based healthcare provider, participants will be dropped from the

study if contact information for an alternative healthcare provider is not obtained.

Intervention Period

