4.7 Data Analysis

Detailed statistical analysis plans (SAP) will be developed prior to completion of primary outcome data collection. Prior to analysis, study population details including the number randomized to each study arm and lost to follow-up will be described. Baseline participant characteristics will be summarized for the SparkRx and eUC arms as means, standard deviations, medians, 25th and 75th percentiles for continuous variables, and as counts and percentages for categorical variables. Differences in baseline characteristics between the groups will be explored using tabular and visual displays, as appropriate, and appropriate statistical tests (e.g., independent sample t-tests for continuous variables, chi-square tests for categorical variables).

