4.7.1 General Approach

Analysis Populations: All analyses will be completed in line with the intention-to-treat (ITT) principle, where all participants will be included in the analyses according to their assigned study arm at baseline, regardless of adherence to study protocol. Per-protocol analyses will also be conducted to estimate treatment effects for participants who adhered to the protocol, and will include individuals who completed the Baseline and post-intervention PHQ-8 assessments and, for participants in the SparkRx group, met a minimum engagement threshold of completing two modules.

Descriptive Statistics: For descriptive statistics, the following will be reported:

Continuous data: n, mean, standard deviation, median and interquartile range, minimum and maximum

Categorical: n/N and percentage of total per arm

Missing Data: We do not anticipate missing data for the stratification variables, which will be included as covariates in the analysis models. Ongoing efforts will be made to reduce the amount of missing data for all outcomes. Despite these efforts, missing data for primary, secondary, and tertiary/exploratory outcomes are likely. Data missing at random (MAR) on dependent variables are easily handled in repeated measures mixed models so no imputation will be needed. For all other statistical analyses described below and missing data on covariates (or independent variables) in models, multiple imputation will be used if at least 5% of data points are missing for a given covariate or variable. Case analysis or single imputation methods may also be used and a specific approach for imputation will be selected based on key attributes of the obtained data, including percent missing and whether data are missing at random. We will compare the results obtained with and without imputation. Sensitivity analyses will be used to assess the impact of potential deviations from the MAR assumption on the study findings.

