4.7.4 Analysis of Tertiary/Exploratory Outcomes

For each continuous outcome (e.g., GAD-7, BAD, PQ-LES-Q), scores at post-intervention will be compared between groups using analysis of covariance (ANCOVA) models, with baseline scores included as a covariate.

To test the hypothesis that legal guardian-reported depression symptoms (PHQ-8 proxy) will be lower for the SparkRx group than the eUC group at post-intervention, we will implement a mixed effect model with appropriate correlation matrix as described above (4.7.2).

Moderation analyses will be carried out to determine if and how participant characteristics (baseline PHQ score, antidepressant medication use, sex/gender, and age) influence intervention effects on PHQ-8 scores at post-intervention. Mediation analysis will be carried out to determine whether intervention engagement (e.g., module completion rate, duration of use, time to complete program) mediates the effect of intervention on PHQ-8 scores at post-intervention.

Changes in healthcare utilization and absenteeism from baseline to post-intervention will be examined descriptively. Ratings of app usability and engagement (SUS, UEF-SF) will be examined descriptively for the SparkRx group only.

Outcomes collected at the 1-month follow-up time point will be analyzed as above.

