7.3 Protection Against Risk

To minimize psychological risks, participants will be instructed that they can choose not to answer any question in any assessment, and can discontinue their participation at any time. Because baseline PHQ-8 score and current antidepressant medication use are required for study randomization, participants will be informed that if they choose not to respond to these questions, they will not be able to continue their participation in the study. In addition, because the SparkRx mobile app progresses in a linear fashion, questions in the mobile program must be answered to progress to the next task. During consent, participants will be informed that they may discontinue their participation at any time. Patient responses to assessments completed weekly will be monitored as well as free response answers to questions delivered via the mobile app. This will enable detection of deterioration in clinical status. If such deterioration occurs, research staff will immediately contact the PI/study clinician/Medical Expert. Participation will be terminated if clinical evidence indicates that continuing would not be in the best interest of the subject as determined by the Medical Expert in consultation with a study clinician. Participation will also be terminated if the Medical Expert determines that the subject's

safety cannot be adequately monitored and/or circumstances would prevent the safety protocol from being implemented (e.g., participant's location cannot be confirmed to be within the U.S., healthcare provider indicates that participant is not their patient and alternative provider information cannot be obtained in a timely fashion). Weekly symptom reporting will also help the research team to identify any psychological or physical health consequences of study participation and, in consultation with study clinicians and the Medical Expert, determine the best way to mitigate further risks to participant health.

No medications will be withheld; however, participants will be asked to report changes to mental health-related treatment while participating in the research study.

To minimize risks to privacy and/or confidentiality, only personnel with training in protecting private information about human subjects will have access to study data. Special care will be taken to prevent unauthorized access to data files.

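### The three PHQ-8 responder outcomes are compared by plain chi-square tests that ignore baseline PHQ-8 and the stratified randomisation, giving up some precision at no saving

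*Combined protocol and SAP*

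**What the plan says.** Section 4.7.3 compares the three secondary outcomes "for each group, and compare rates between groups using chi-square tests". It names no covariate, stratum, between-arm effect measure or confidence interval. Section 4.7.4 extends the approach to the later visit: "Outcomes collected at the 1-month follow-up time point will be analyzed as above".

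Elsewhere the plan does use baseline information:

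- Section 3.1: "Randomization will be stratified by participant-reported antidepressant medication status", and also by baseline PHQ-8 below 15 versus 15 or above.
- Section 4.7.2, on the primary model: "baseline PHQ-8 score, and antidepressant medication status (variable used for randomization) will be included in the model as fixed effects".
- Section 4.7.1: "We do not anticipate missing data for the stratification variables, which will be included as covariates in the analysis models".
- Section 4.7.4, on the continuous exploratory outcomes: "using analysis of covariance (ANCOVA) models, with baseline scores included as a covariate".

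**The concern.** The outcomes ranked directly below the primary get a less efficient analysis than the exploratory scales. The general sentence in 4.7.1 does not help, because a chi-square test takes no covariates.

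This is not an error: the tests are valid and the primary analysis is untouched. What is at stake is precision. A strong predictor, known for everyone, is left out of the comparison. In addition, the usual chi-square standard error takes no credit for the balance that stratified randomisation has already produced. Nor does the plan commit to an effect estimate with an interval, which readers will want more than a p-value.

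**Working it through.** **1. The plan's own figure.** Section 4.6 uses d = 0.4, two-sided alpha 0.05 and 80% power. Per arm, n = 2(z₀.₉₇₅ + z₀.₈₀)²/d² = 2(1.960 + 0.842)²/0.16 = 98.1, rounded up to 99, or 198 in total against the stated 200. Power at 100 per arm is 0.807 (0.804 with the t distribution). The figure reproduces. With 220 enrolled and 10% lost, 220 × 0.9 = 198 are analysed. The plan gives no power for the secondary outcomes.

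**2. What each outcome demands at a given baseline.** Entry requires a score of at least 5 (section 2.5) and the scale ends at 24 (section 3.4).

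| Baseline | Remission (<5): drop needed | 5-point reduction: final score at most | 50% response: final score at most |
|---|---|---|---|
| 5 | 1 | 0 | 2 |
| 14 | 10 | 9 | 7 |
| 15 | 11 | 10 | 7 |
| 24 | 20 | 19 | 12 |

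The drop needed for remission runs from 1 to 10 points within the low stratum and from 11 to 20 within the high one. Continuous baseline should therefore recover more than the two-level stratum. Response already scales with baseline, so little gain is expected there.

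**3. Main simulation.** From the documents: 1:1 allocation, four strata, d = 0.4, 220 randomised, 10% loss. Assumed, because the documents do not say: baseline mean 10, 12 or 14 with SD 4.5, limited to 5–24; baseline-to-post correlation 0.4, 0.5 or 0.6; eUC improvement 2 or 3 points; 30% on antidepressants; blocks of 4; loss at random. That makes 3 × 3 × 2 = 18 scenarios of 3,000 trials each. The effect is 0.4 × 4.5 = 1.8 points.

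Three tests were compared: Pearson chi-square; Cochran-Mantel-Haenszel (CMH) over the four strata; and the score test for arm in logistic regression on arm, continuous baseline PHQ-8 and antidepressant status. Gains are in power points over chi-square. The central case has mean 12, correlation 0.5 and improvement 2.

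| Outcome | Chi-square power | Gain, CMH | Gain, adjusted score test | Central case, chi-square to adjusted |
|---|---|---|---|---|
| Response | 54–78% | −0.8 to +0.2 | −0.2 to +0.8 | 64.3 to 64.7% |
| Remission | 31–63% | +0.5 to +2.3 | +1.3 to +7.5 | 44.7 to 48.0% |
| 5-point reduction | 54–74% | +0.7 to +4.5 | +3.4 to +7.5 | 60.7 to 66.3% |

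**4. Second simulation, other assumptions.** 100 per arm, baseline centred at 12.5, post SD 5, and the test based on the standardised risk difference. Power in %, chi-square to adjusted:

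| Correlation, eUC drop | Response | Remission | 5-point reduction |
|---|---|---|---|
| 0.3, 3 points | 63.1 to 64.2 | 51.4 to 53.4 | 55.3 to 62.2 |
| 0.5, 3 points | 70.4 to 70.7 | 51.3 to 56.2 | 67.6 to 71.6 |
| 0.7, 3 points | 80.8 to 82.5 | 52.3 to 63.8 | 86.2 to 87.2 |
| 0.5, 5 points | 74.8 to 74.2 | 58.7 to 64.9 | 62.6 to 68.3 |

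The gains are −0.6 to +1.7 (response), +2.0 to +11.5 (remission) and +1.0 to +6.9 (5-point reduction). As correlation rises, remission gains more and the 5-point reduction less.

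**5. In participants.** In the main simulation the smaller variance of the risk difference is worth about 5–19% more participants for remission and 11–23% for the 5-point reduction. The second simulation, judged by the spread of the estimates over trials, gives less. Its adjusted-to-unadjusted variance ratios are 0.873–0.984 (remission) and 0.931–0.980 (5-point reduction), so 1/ratio − 1 is 2–15% and 2–7%.

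**6. Type I error.** In the main simulation's null scenarios chi-square rejects on average 5.0% (response), 4.7% (remission) and 4.2% (5-point reduction). The adjusted score test rejects 4.1–6.0% across scenarios (Monte Carlo SE 0.4), and a separate run gave 4.5–6.3% for the standardised risk difference. With rare remission, 8,000 null trials gave 5.9% and 6.1%.

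**7. A trap.** A Wald test on the log odds ratio can lose up to 4.1 power points for remission when eUC remission is only 4–5%.

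**The case against.** These are supportive dichotomies of a score that the primary model already analyses with adjustment. A chi-square on n/N is transparent and common, and a later SAP could add an effect estimate. That is fair, and it makes this an optional improvement. But 4.7.3 names the chi-square test explicitly, so the default is that the SAP will repeat it.

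The size of the gain rests on assumed inputs. This stands: +3.4 is not a floor for the 5-point reduction, which gains only about 1 point at correlation 0.7 in the second simulation.

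Section 4.7.1 calls for multiple imputation outside the mixed models once at least 5% is missing, and 10% attrition is expected. The likely analysis is therefore an imputed one, although the section also leaves room for case analysis. No imputed analysis, adjusted or not, was simulated, so the gain there is untested. This stands too.

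Finally, the adjusted tests can be slightly liberal when remission is rare, at about 6%. A score-test p-value and a risk-difference interval can also disagree near the 5% boundary. Both are minor, but the SAP author should know of them. None of these points reverses the direction of the gain.

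**Conclusion.** The concern holds as a low-cost gain in precision, not as a defect. At the planned size, adjustment adds a modest amount of power for remission (+1.3 to +11.5 points across the two simulations) and for the 5-point reduction (+1.0 to +7.5), and essentially nothing for response (−0.6 to +1.7). CMH recovers only part of this. Type I error stays close to 5%, with up to about 6% seen in individual scenarios.

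Confidence is high in the direction and low in the exact size. The size depends on baseline distribution, correlation and event rates that the documents do not give, and on complete-case analysis with loss at random. Which of the two outcomes gains more depends on the same unknowns.

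**What to change.** In 4.7.3, or in the detailed SAP, write:

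> Each secondary outcome is compared between arms by logistic regression on arm, baseline PHQ-8 (continuous) and antidepressant status, with a score test for arm. The effect is reported as a standardised risk difference with 95% CI. If multiple imputation is used, the standardised risk difference is pooled by Rubin's rules and tested by its pooled standard error. Raw n/N and percentages by arm are shown as description. The same analysis applies at 1-month follow-up.

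State which result governs if the score test and the interval disagree, and do not use a Wald test on the log odds ratio. A simpler option is a CMH test with a Mantel-Haenszel risk difference over the four randomisation strata. As a separate clarification, say in 4.7.4 whether the exploratory ANCOVAs also include antidepressant status.

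The cost is wording only. Section 7.3 confirms that both covariates are collected before allocation: "Because baseline PHQ-8 score and current antidepressant medication use are required for study randomization". The SAP is still to be written: "Detailed statistical analysis plans (SAP) will be developed prior to completion of primary outcome data collection". The choice should be fixed before anyone sees outcomes by arm, since adjustment chosen later would look data-driven.
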